## 2. OBJECTIVES, OUTCOMES MEASURES AND HYPOTHESES

OBJECTIVES	OUTCOME MEASURES	HYPOTHESES
Primary objective  To examine the effect that an information-based intervention (energy labelling)	Energy (kcal) of the ordered meal.	An increased availability of lower energy menu options will result in a decrease in total

and a structural intervention (increased availability of lower kcals options) have on kcals ordered in a hypothetical meal ordering task among participants of lower and higher SES.
		
energy ordered among both participants of lower and higher SES. However, energy labelling may exert a stronger effect on energy ordered among participants of higher vs. lower SES.

Secondary objectives
 
To examine the reasons why the effects that energy labelling have on kcals ordered may vary based on a participants' SES.
 
To examine the effect of labelling on familiar and unfamiliar cuisines menus.
	
Health motivation in food choices (questionnaire score).
 
Energy (kcal) of the ordered meals for familiar and unfamiliar cuisines.
	
The participants of higher SES will be more motivated by health in their food choices than participants of lower SES, which will mediate the relationship between SES and the effect of energy labelling on the total energy ordered.
 
Energy labelling will have a greater effect for unfamiliar compared to familiar cuisines.

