### 3. EXPERIMENTAL DESIGN

Participants will be enrolled in an online survey and make hypothetical menu choices. Participants will be randomized into a mixed-design experiment with 2x2 between-subjects conditions with factors of kcal labelling (absent vs. present) and availability (baseline availability of main dishes with  $\leq 600$ kcals vs. higher availability of main dishes with  $\leq 600$ kcals) and 6 repeated measures (3 familiar and 3 unfamiliar menus).

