## 7. STATISTICAL ANALYSIS

All statistical analyses will be performed using SAS version 9.3 (SAS Institute, Inc., 2012 SAS® 9.3. Cary, NC). The level of significance will be set at  $p < 0.05$ . Linear mixed models will be fitted with PROC MIXED.

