### 7.4. Main analyses

The measure of SES used in our primary analysis will be the *highest educational qualification* (categorical variable: *lower vs. higher*) because previous research showed that people with college education were more likely to use kcal labels at restaurants [37]. The measure of health motivation will be the response to the first item from the Single-item Food choice Questionnaire: “It is important to me that the food I eat on a typical day is healthy”, i.e., importance of healthiness.

First, we will examine whether our manipulation of familiarity is valid by examining the proportion of participants that are familiar / unfamiliar with each cuisine menu type (i.e. we expect >75% of participants to be familiar with our chosen ‘familiar’ cuisines and <25% of participants to be familiar with our ‘unfamiliar’ cuisines). We will also report the mean and SD of the *familiarity score* for each cuisine.

A linear mixed model will be used to test the effect of *labelling* (categorical, between-subject), *availability* (categorical, between-subject), *highest educational qualification* (categorical, between-subject), *familiarity* (categorical, within-subject) and *labelling\*highest educational qualification*, *availability\*highest educational qualification*, *labelling\*familiarity*, *availability\*familiarity*, interactions on *energy of the main* for the six dining out scenario. A random effect of participant will be added by using an unstructured covariance structure to account for correlation between repeated ordering by the same participant.

If any interactions with *familiarity* are significant, analysis will be stratified by *familiarity* and two linear mixed models will be fitted to examine the effect of *labelling*, *availability*, *highest educational qualification* and *labelling\*highest educational qualification*, *availability\* highest educational qualification* interactions on *energy of the main* for familiar and unfamiliar cuisines with participant effect as random to account for correlation between repeated ordering by the same participant for familiar and unfamiliar cuisines.

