If the above analyses reveals a significant interaction between *labelling* or *availability* condition and *highest educational qualification* on *energy of the main*, analysis will be stratified by *highest educational qualification (lower vs. higher)* and two linear mixed models will be fitted to examine the effect of *labelling* and *availability* on *energy of the main* for lower and higher educational qualifications.

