#### Debriefing questionnaire

We will finally explore whether the restaurants menus are valid and the extent to which participants reported using kcal information when making food choices. Responses to the debriefing questionnaire will be analysed:

- We will describe the responses to each item (mean, SD, % agree [5, 6, 7], % disagree [1, 2, 3]) in the overall sample to characterise *validity of menu design, validity of food offer, kcal influence*.
- Three linear mixed models will be used to test the effect of *labelling, availability, familiarity* and *highest educational level* on the three dimensions of the debriefing questionnaire (a) *validity of menu design*, (b) *validity of food offer*, and (c) *kcal influence* to investigate whether the responses differ across experimental conditions and SES.

To account for multiple testing the alpha level for secondary analyses will be set at  $p = 0.01$ .

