### 7.6. Sample size

The best available evidence of the effect of kcal labelling on kcal ordered at restaurants is the meta-analysis of Crockett et al. 2018. The authors analysed the effects of 3 RCTs testing energy labelling in restaurants [21]. They demonstrated a statistically significant reduction of 47 kcal in energy purchased when menus were labelled. The weighted average kcal ordered in the no label condition was 706 kcal. These results suggest that we could expect a 7% energy reduction in the labelling condition compare to the control condition. Previous studies examining the effect of an increased availability of lower-energy products on food selection tend to produce similar or larger effects than kcal labelling tends to [39], [40].-In a previous trial we ran at virtual fast food restaurants ([osf.io/ajcr6](https://osf.io/ajcr6)), we found a between-subject variance of 47,224 for kcal ordered ( $SD = 217.3$ ).

In a two-level mixed model, including 6 observations per participant at level 1 and estimating a level 1 and level 2 variance of 47,244 for energy of the main, a sample size of 1,000 participants with  $\alpha = 0.05$  allows to detect 2% energy reduction and above at power = 0.93 due to labelling and/or availability, an additional 2% energy reduction (or above) in participants of higher educational qualification at power = 0.81 due to an interaction between labelling and highest educational qualification and/or an interaction between availability and highest educational qualification, an additional 2% energy reduction (or above) for unfamiliar menus at power = 0.86 due to an interaction between labelling and familiarity and/or an interaction between availability and familiarity (MLPowSim) [41].

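### A significant familiarity interaction reopens the education interactions in each cuisine half at 0.05, giving the primary labelling-by-education hypothesis up to three unadjusted tests

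*Combined protocol and SAP*

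**What the plan says.** Section 2 places the equity hypothesis under the primary objective: "energy labelling may exert a stronger effect on energy ordered among participants of higher vs. lower SES". Education (lower or higher) is the SES measure in the primary analysis.

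Section 7.4 fits one linear mixed model to the energy of the main dish over six menus. It contains labelling-by-education, availability-by-education, labelling-by-familiarity and availability-by-familiarity. It has no three-way term.

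The next step is conditional: "If any interactions with *familiarity* are significant, analysis will be stratified by *familiarity* and two linear mixed models will be fitted". Each of the two models again contains both education interactions.

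A further step begins "If the above analyses reveals a significant interaction between" and stratifies by education if labelling or availability interacts with education. Its wording covers the all-cuisine model and both cuisine-specific models, and nothing says which of the three decides.

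On error control, section 7 says "The level of significance will be set at" p < 0.05. The only adjustment is at the end of section 7.5: "To account for multiple testing the alpha level for secondary analyses will be set at" 0.01. The cuisine-specific models sit in section 7.4, under the main analyses, so that adjustment does not reach them.

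**The concern.** Following a significant labelling-by-familiarity term with labelling effects by cuisine type is ordinary practice. Here the follow-up does more. A significant familiarity interaction says nothing about whether labelling works differently by education, yet it opens four new education tests: two interactions in each of two halves. The labelling-by-education hypothesis can then be declared positive from the all-cuisine model, the familiar model or the unfamiliar model, each at 0.05.

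Without a labelling-by-education-by-familiarity or availability-by-education-by-familiarity term, an education interaction found in one cuisine type and not the other would rest on one p-value below 0.05 and another above it.

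A false result would also travel. It triggers the education-stratified models in section 7.4. If read as a main-analysis interaction, it also triggers the moderated mediation in section 7.5, which is meant to explain the inequality.

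**Working it through.** **Inputs**

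- Variance 47,244 at level 1 and at level 2; 1,000 analysed participants (section 7.6).
- Three familiar and three unfamiliar menus per participant (section 3).
- Equal allocation to four arms, so 500 versus 500 for labelling (section 6).
- Education 40% lower, 60% higher. This is an assumption, taken from the 10% + 30% recruitment targets in section 4.1. The null error rates below do not depend on it; the kcal values in step 5 do.
- Reference energy 706 kcal (section 7.6), so 2% = 14.1 kcal and 7% = 49.4 kcal. No baseline for the main dish alone is given.
- Two-sided tests (assumed; the plan does not say).

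**1. The plan's figure for the gate.** Section 7.6 states power 0.86 for an additional 2% reduction on unfamiliar menus. The standard error of labelling-by-familiarity is sqrt(4 × (4 × 47,244/6)/1,000) = 11.2 kcal. Then 14.12/11.2 = 1.26, and power is about 0.24. The stated 0.86 does not reproduce from these inputs, so it is not used here.

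**2. Correlation between the halves.** A participant's mean over three menus has variance 47,244 × (1 + 1/3), and the two half-means have covariance 47,244. The correlation is 1/(4/3) = 0.75.

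**3. Error rate once the split is triggered.** With a true labelling-by-education effect of zero, simulation of two standard normal half-estimates with correlation 0.75, and their pooled estimate, gives:

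| Tests counted | Chance of at least one false positive |
|---|---|
| All-cuisine model only | 0.050 |
| Either half | 0.081 |
| Any of the three | 0.083 |

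The any-of-three rate is 0.115 at intraclass correlation 0, 0.100 at 0.2 and 0.074 at 0.7. Three independent tests would give 1 − 0.95³ = 0.143.

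**4. Error rate over the whole path.** The gate opens if either familiarity interaction is significant. The gate statistics are uncorrelated with the education estimates, so the rate is 0.05 + P(gate) × (0.083 − 0.05). Availability-by-familiarity is taken as null, so P(gate) = 1 − 0.95 × (1 − power of labelling-by-familiarity).

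| True labelling-by-familiarity | P(gate) | Whole-path error |
|---|---|---|
| 0 kcal | 1 − 0.95 × 0.95 = 0.0975 | 0.053 |
| 14 kcal (2%) | 1 − 0.95 × 0.76 = 0.28 | 0.059 |
| 49 kcal (7%) | 1 − 0.95 × 0.007 = 0.99 | 0.083 |

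**5. Discordant halves.** Suppose the true education interaction is the same in both halves. The standard error of labelling-by-education is sqrt(4 × 47,244 × (7/6)/(1,000 × 0.24)) = 30.3 kcal pooled, and sqrt(4 × 47,244 × (4/3)/(1,000 × 0.24)) = 32.4 kcal per half. In triggered trials:

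| True interaction | Share of 706 kcal | Pooled power | Exactly one half significant |
|---|---|---|---|
| 0 kcal | 0% | 0.05 (type I error) | 6% |
| 14 kcal | 2% | 0.08 | 8% |
| 59 kcal | 8.4% | 0.50 | 23% |
| 85 kcal | 12% | 0.80 | 18% |

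**The case against.** The strongest reply is that everything is pre-specified: the gate, the models and the follow-ups are fixed in advance, and stratifying after a significant interaction is common. The plan nowhere says that one half alone confirms the hypothesis. The inflation is also modest: at the plan's own 2% effect the whole-path error is 5.9%, and reaching 8.3% needs a familiarity interaction near 49 kcal. That is 7% of 706 kcal, a figure that section 7.6 derives for the labelling main effect, not for an interaction.

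The point about size stands, and the unconditional rates belong beside the 8.3%. Pre-specification does not settle the matter, because the rules as written act on a hit in any of the three models at 0.05. If the two halves were read as replacing the all-cuisine model, the triggered rate would still be 8.1%.

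Three stronger readings are tempting and not supported.

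- *No difference between the halves is ever tested.* This is too broad. Differences in the labelling and availability effects are tested; they are the gate. Only differences in the education interactions go untested.
- *The plan expects the split, given its 0.86 power.* That power does not follow from the plan's own variances. What can be said is that section 2 hypothesises a larger labelling effect for unfamiliar cuisines, so the trigger is a hypothesised outcome.
- *The primary equity error is about 16%.* That counts both education interactions (1 − 0.917² = 0.16, against 1 − 0.95² = 0.098 for the two pooled tests). Section 2 hypothesises an SES difference for labelling only; for availability it expects a reduction in both groups.

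**Conclusion.** The concern holds in a limited form. The labelling-by-education hypothesis gets up to three unadjusted tests through a gate unrelated to education, and a difference between cuisine types in the education interactions has no test. The false-positive rate is about 8.3% if the split is triggered, and between about 5.3% and 8.3% over the whole path, depending on the true familiarity interaction. These figures rest on equal variances at the two levels, two-sided tests and a normal approximation.

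The risk of a spurious cuisine-specific finding is real but depends on the effect. The 18–23% discordance needs true education interactions of about 59 to 85 kcal, far above the 2% the plan targets; at 14 kcal it is about 8%, against 6% with no effect. The plan does not announce a cuisine-specific inequality claim; it leaves room for one without a test to support it. The change should be made before analysis because it is cheap and bears on a primary hypothesis.

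**What to change.** In section 7.4:

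- Name the all-cuisine model as the only confirmatory test of labelling-by-education and availability-by-education.
- If a familiarity interaction is significant, report the labelling and availability effects for familiar and unfamiliar cuisines as contrasts from that same model, which already contains the terms needed.
- If education interactions by cuisine type are wanted, add the two three-way terms and label these results exploratory. They should not trigger the education-stratified models or the moderated mediation in section 7.5.
- In the step that stratifies by education, replace the reference to the preceding analyses with a reference to the all-cuisine model.

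Using the labelling-by-education-by-familiarity term merely as a new gate would not be enough. If the half-specific tests still counted, the error rate would be about 6.0%. Bonferroni over the three tests (0.0167 each) would control it, but conservatively, at about 2.9% with the plan's variances.

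The cost is a few sentences of SAP text and some contrast statements, with no new data. The downside is that cuisine-specific education effects become exploratory.

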#### Menus

The design of the restaurant menus will be based on menus from existing US restaurants. In a recent study, 1,184 American adults were asked which of 34 national cuisines they had tried and whether

they liked or disliked them [26]; results are summarised in **Appendix B**. Based on these results we selected three familiar (tried by at least 90% of US people: American, Mexican and Italian cuisines) and three unfamiliar cuisines (never tried by approximately 50% of US people: Lebanese, Peruvian, Moroccan cuisines) for American people. Using the online menus of US restaurants offering the selected cuisines, we will then create sample menus for the six distinct restaurant cuisines, each consisting of 10 main dishes and a selection of between 5 sides and 5 desserts (including actual food names, description and prices).

For familiar cuisines, the menu-model restaurants will be US popular chain restaurants (>800 outlets across the country); for unfamiliar cuisines, they will be US restaurants offering these specific types of cuisines that will be chosen by searching for restaurants in large US cities: New-York, Los Angeles, Chicago, Houston (using Yelp, Tripadvisor). All the food items (and their description) included in the experimental menus will be based on existing US restaurants. Because kcal labelling is only mandatory for restaurant chains in the US, we will use external sources to calculate the energy content per 100g of the menu options available for unfamiliar cuisines (e.g., online recipes, national food composition databases). All the six menus will offer a similar range of main options in terms of energy content (i.e., similar min, median and max).

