### Interventions

LE options are main dishes ≤600 kcal because meals ≤600 kcal comply with the dietary recommendation for US adults (i.e., on average 2,000 kcal per day) assuming an energy repartition pattern of three main meal occasions, each accounting for 20–35 % of daily energy intake, and 1–2 snacking occasions, each accounting for 5–10 % of daily energy intake [27].

In the baseline availability conditions (C and CL) 1/10 main dishes on the menus will be 600 kcal or less and 9/10 will exceed 600 kcal. In the increased availability of lower energy options conditions (A and AL), the proportion of main dishes ≤ 600 kcal will be increased to 5/10 by replacing four of the > 600 kcal main dishes from the baseline availability conditions with lower energy main dishes, whilst holding the price of replaced menu items the same. The menu items with the highest and the lowest energy content will remain the same in order to ensure the range of energy is consistent across conditions. The difference in the mean energy content of the menus items between C/CL and A/AL conditions will be approx. the same for familiar and unfamiliar menus.

In the energy labelling conditions (L and AL) energy in kcal will be added next to each menu option and reference information on energy requirements will be displayed. The energy labelling format will be in line with the mandatory menu labelling policy published by the US Food and Drug Administration [28], which requires restaurants to:

- Disclose calories for standard menu items listed on menus and menu boards:
  - Calorie labelling is placed on the menu adjacent to the name or the price of the menu item in a manner in close proximity and clearly associated with the menu item;
- Include on menus a succinct statement concerning suggested caloric intake and a statement that additional nutrition information is available upon request:
  - The succinct statement ‘2,000 calories a day is used for general nutrition advice, but calorie needs vary’ must appear on the bottom of menu boards and at the bottom of each page of multi-page menus;

- The statement of availability 'Additional nutrition information available upon request' must appear on the bottom of the first page of a menu that lists standard menu items and at the bottom of the menu board

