#### **Cuisine familiarity**

- Familiarity condition: Binary variable based on the experimental design: 0 for unfamiliar cuisines and 1 for familiar cuisines
- Familiarity score: Ordinal variable based participants answer for each cuisine to the question "Have you ever tried [6 cuisines]?" coded as 1: Never tried; 2: Not in the last year; 3: Less than once per month; 4: 1-3 times per month; 5: 1-2 times per week; 6: 3 times per week or more

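### The familiarity interactions compare two specific sets of three menus and do not, by themselves, support a claim about unfamiliar cuisines in general

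*Combined protocol and SAP*

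**What the plan says.** The second secondary hypothesis in section 2 is stated for cuisines as a class: "Energy labelling will have a greater effect for unfamiliar compared to familiar cuisines". It concerns labelling. No matching hypothesis is given for availability, although section 7.4 tests both interactions.

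The Menus part of section 5.1 says how the classes were filled: "we selected three familiar (tried by at least 90% of US people: American, Mexican and Italian cuisines) and three unfamiliar cuisines", the latter being Lebanese, Peruvian and Moroccan. Section 7.2 then fixes familiarity as an attribute of the cuisine: "Familiarity condition: Binary variable based on the experimental design: 0 for unfamiliar cuisines and 1 for familiar cuisines".

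The section 7.4 model contains labelling, availability, education, familiarity and four two-way interactions. On the random part it says: "A random effect of participant will be added by using an unstructured covariance structure". It has no term for cuisine and none for cuisine by intervention. On a significant familiarity interaction, "If any interactions with *familiarity* are significant, analysis will be stratified by *familiarity* and two linear mixed models will be fitted". Section 7.5 uses the same result to decide how mains are averaged for the mediation analysis.

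Two design controls bear on the point. The Menus part matches the six menus on minimum, median and maximum energy. Of the two kinds of menu, the Interventions part says: "The difference in the mean energy content of the menus items between C/CL and A/AL conditions will be approx. the same for familiar and unfamiliar".

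**The concern.** Familiarity varies only between menus, three against three. Label and availability effects may differ from menu to menu for reasons unrelated to familiarity, such as which dishes are popular, how energy is spread over the ten mains, or which four dishes were replaced. The planned standard error reflects noise between participants and between orders, and nothing else. It shrinks as participants are added. The uncertainty that comes from having three menus per class does not.

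At stake is the wording of a secondary conclusion. A significant interaction would naturally be reported as evidence that labelling works differently for unfamiliar cuisines, when one unusual menu among six could have produced it. The sensitivity analyses in section 7.4 (excluding participants who guess the aim, and replacing the education variable) do not look at single cuisines, and the familiarity score is only described.

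**Working it through.** **Inputs.** From section 7.6: 1,000 participants, six orders each, level 1 and level 2 variance 47,244 (the sentence before gives 47,224; the gap is immaterial here), reference intake 706 kcal, labelling effect 47 kcal. From section 6: equal allocation to four conditions, hence 500 v 500 for each factor. From section 7: alpha 0.05, taken as two-sided. Assumed, because the documents give no value: tau, the SD between menus of the intervention effect.

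**1. Standard error of the planned interaction.** For each participant take the mean of three familiar mains minus the mean of three unfamiliar mains. The participant effect cancels, leaving variance 2 × 47,244 / 3 = 31,496. Between 500 and 500 participants, SE² = 31,496 × (1/500 + 1/500) = 125.98, so SE = 11.22 kcal.

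**2. The plan's own figure.** Section 7.6 gives power 0.86 for an additional 2% reduction on unfamiliar menus. With 2% of 706 = 14.1 kcal and SE 11.22, power is 0.24 two-sided (0.35 one-sided). The 0.86 does not reproduce; at this SE it would need about 34 kcal. That is a separate matter and nothing below depends on it.

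**3. Rejection when familiarity has no effect.** If menu effects vary with SD tau, each class average carries extra variance tau²/3. With both classes treated as samples of menus, the true SD of the contrast is √(125.98 + 2·tau²/3). With only the unfamiliar class so treated, it is √(125.98 + tau²/3). The test still uses 11.22, so the rejection rate is 2 × [1 − Φ(1.96 × 11.22 / true SD)].

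| tau (kcal) | both classes: true SD, rejection | unfamiliar only: true SD, rejection |
|---|---|---|
| 0 | 11.22, 5.0% | 11.22, 5.0% |
| 5 | 11.94, 6.5% | 11.59, 5.8% |
| 9 | 13.42, 10.1% | 12.37, 7.5% |
| 20 | 19.82, 26.7% | 16.10, 17.2% |

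Simulation of the random-intercept model with education terms left out (4,000 runs per setting, both classes sampled) gave 5.2% at tau = 0, 6.8% at 5 and 25.4% at 20 for labelling, in line with the formula.

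**4. The same test for these six menus only.** With menu effects unequal but class averages held equal, simulated rejection was 4.4% to 5.3%. For that narrower question the planned test keeps its level.

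**5. One atypical menu.** If one menu's labelling effect differed by 47 kcal from the other five, the contrast would move by 47/3 = 15.7 kcal and be significant about 29% of the time. No planned output would identify that menu.

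**6. A cuisine-level test.** A t-test on the six cuisine-specific effects (4 df) held 4.7% to 5.7% at every tau simulated. Its power at 14.1 kcal, from the noncentral t, is 0.165 at tau = 0, 0.13 at 9 and 0.09 at 20.

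**The case against.** **The test is sound for what it compares.** A reader might infer that it assumes equal effects on all three menus of a class, or that it is invalid. Step 4 shows otherwise: it tests equality of two class averages. The issue is only how far the conclusion reaches. This stands.

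**The cuisines were chosen by rule, not drawn at random.** In Appendix B only American, Mexican and Italian (8%, 8% and 9% never eaten) meet the 90% rule; the next, Chinese, is at 13%. At cuisine level the familiar class is complete, which is why the lower column of rates is shown. The unfamiliar class is a selection: eleven cuisines lie between 49% and 53% never eaten, and three were used. Menu construction within a cuisine also remains a choice. This reduces the concern without removing it.

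**Tau is unknown.** At 5 kcal or less the effect is minor. A reader might infer a large tau from Appendix A: on the American menu, replacing four of the eight middle dishes by dishes assumed to average 485 kcal lowers the menu mean by anything from 134 to 278 kcal. That does not support a value. It takes the extremes of hypothetical swaps in one menu, the plan matches the mean shift between the two classes, and a shift in menu mean is not an effect on choice. It says nothing about labelling.

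**The follow-on steps are reasonable.** If effects differ between the two menu sets, for whatever reason, stratifying the model and averaging separately is defensible. This stands; only the general wording is exposed.

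**Requiring a cuisine-level test would make the hypothesis almost untestable.** At the 2% target its power is at most 0.165 (step 6), so it should not be a condition for the claim. This also stands.

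Reading the unstructured covariance as a 6 × 6 matrix rather than a random intercept does not answer the point, since neither adds a menu-by-intervention term.

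**Conclusion.** The point holds in a limited form. The familiarity interactions in section 7.4 are valid comparisons of two sets of three menus. They are not, by themselves, tests of the general hypothesis in section 2. For that wider claim the 5% level is exceeded by an amount set by tau: from about 6% to 6.5% at 5 kcal, through 7.5% to 10% at 9 kcal (about a fifth of the 47 kcal labelling effect), to 17% to 27% at 20 kcal.

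These figures rest on the variances in section 7.6, two-sided 5% testing and an assumed tau. Leaving menu means in the residual offsets the excess slightly: with an assumed menu-mean SD of 100 kcal and tau = 14.1, simulated rejection was about 14% rather than 16% to 18%. The documents do not support saying that a familiarity finding would be false, or that menu differences will be reported as familiarity; they can be, at a rate nobody can yet state. The primary main effects and education interactions are not in question. This is a cheap improvement to a secondary conclusion.

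**What to change.** In section 7.4, keep the planned model and both familiarity tests, and add the following.

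1. A supporting model with cuisine nested in familiarity as a main effect, plus labelling*cuisine and availability*cuisine within class. Six cuisine effects less two class averages gives 4 df for each interaction. The cuisine main effect is needed; without it the interaction terms would also absorb differences in mean energy between menus.
2. The six cuisine-specific labelling effects and six availability effects, each with a 95% CI.
3. A wording rule: a significant familiarity interaction is reported as a difference between these two sets of three menus, unless the cuisine-specific effects are consistent within each class. State in advance how consistency will be judged.
4. Optionally, the 4-df t-test on the six effects as a sensitivity analysis, not as a condition for the claim.

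The cost is one extra model on data already collected, with no more participants, and a secondary conclusion that may be narrower. The cuisine-specific effects will be imprecise. On the section 7.6 variances each has SE √(94,488 × 4/1,000) = 19.4 kcal, or about ±38 kcal, so they can expose a menu that stands well apart but cannot prove that menus of one class behave alike.
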